9.1 PRIMARY EFFICACY OUTCOME

The primary efficacy variable will be the change from baseline in weekly average API (WAAPI), and the primary timepoint will be Week 12.

9.2 DERIVATION OF THE PRIMARY EFFICACY VARIABLE

WAAPI scores will be calculated for each weekly interval (i.e., 7-day intervals) relative to randomization date (first randomized treatment date) for all subjects (both subjects on q1w and q4w). For example, WAAPI at Week 0 will be the average of available (non-missing) APIs captured during the 7 days prior to Treatment Day 1 (the first randomized treatment day). WAAPI at Week 1 will be the average for the next 7 days including the score captured on Day 1. WAAPI at Week 12 (the primary timepoint) will be the average for the APIs captured from Day 78 to Day 84. The baseline WAAPI score will be the WAAPI at Week 0. The changes from baseline at any post-baseline timepoint will be calculated as baseline minus post-baseline, so that a positive change is indicative of improvement.

9.3 PRIMARY ANALYSIS

The primary analysis will be performed based on the mITT Population.

WAAPI over time will be performed by longitudinal data analysis using mixed-model repeated measures (MMRM) methods. All post-randomization baseline observations will be utilized; missing values will remain as missing (i.e. no attempt will be made to impute missing values, and only observed values will be used in the data analysis). The model will include treatment, post-baseline weeks, treatment by week interaction as fixed effects, and baseline WAAPI as the covariate. The covariance will assume to be unstructured. If the estimates do not converge, SAS default covariance structure (variance components) will be assumed. The MMRM with maximum likelihood estimation will utilize the following pseudo-SAS code for analysis:

```
proc mixed data = WAAPI Data method = ml;
class treatment week subject;
model Change in WAAPI = treatment week treatment*week baseline;
repeated week / subject = subject type = un;
lsmeans treatment / pdiff cl e;
lsmeans treatment*week /slice = week cl diff;
ods output diffs = alldiff;
```

If the estimation under type=un cannot converge, the SAS default (variance components) will be used. The estimated treatment effects, treatment differences, and the two-sided 95% confidence intervals of the treatment differences at all post-baseline timepoints will be presented. The primary comparison will be the treatment difference at Week 12.

A clear advantage of using MMRM is that this method does not require artificial missing imputations that would often create biases. The MMRM method is valid if the “missing at random” assumption holds. The trial is designed to minimize missing values: (a) Subjects who discontinue taking study medication are permitted to remain in the study, and safety and efficacy data will continue to be collected from these subjects; (b) Liberal use of rescue medication is allowed during the study, and data collection will continue even after subjects take these medications, and (c) Robust efficacy data collection procedures will be used in the trial.

Using the procedures above, it is expected that missing values will be minimal and that “missing at random” is a reasonable assumption. Therefore, the “MMRM without missing” imputation is reasonable. Sensitivity analyses of missing value imputations will be performed to support the robustness of the conclusion (see [Section 9.4](#)).

Additional analyses outlined in the sensitivity analyses section ([9.4](#)) will be performed to assess the robustness of the analysis results.

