8.3. Method of Assigning Subjects to Treatment Groups

Randomization will be used to avoid bias in the assignment of subjects to treatments, to increase the likelihood that known and unknown subject attributes (e.g., demographics, baseline characteristics) are evenly balanced across treatment groups, and to enhance the validity of statistical comparisons across

treatment groups.

Subjects who provide written informed consent will be assigned a unique number in the screening process. This number will be used to identify the subject throughout the study.

Subjects who meet the eligibility criteria will be randomized in a 1:1 ratio (Group 1: active CAM2038 SC injections or Group 2: placebo SC injections). Randomization will be stratified based on double blind dosing regimen. Subjects randomized at a titration dose of either 4, 8 or 12 mg will remain on weekly doses. Subjects randomized at a titration dose of 16, 24, or 32 mg will transition to monthly dosing.

Therefore, there will be four different dose types.

- A1 – Active weekly
- B1 – Placebo weekly
- A4 – Active monthly
- B4 – placebo monthly

Due to the size of the study, it is expected that subjects will be balanced for various other baseline factors, including age.

Once any subject number or randomization number is assigned, it cannot be reassigned to any other subject. This study will use central randomization, as described in Section 9.2.

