11.4. Determination of Sample Size

It is estimated that 170 subjects per treatment group will provide 90% power with a 2-sided test at a 5% significance level and standard deviation of API at Week 12 of 2.0 to detect a treatment effect of 0.7 unit (or a standardized effect of 0.35) in change from baseline in the WAAP scores at Week 12 (Double-Blind Phase). Considering a titration success rate of 60%, this study will enroll approximately 875 subjects to obtain 340 subjects achieving a successful dose in order to be randomly assigned to study drug treatment in the Double-Blind Phase.

Additional statistical details will be outlined in the SAP.

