4.4 RANDOMIZATION AND BLINDING

Randomization will be used to avoid bias in the assignment of subjects to treatment, to increase the likelihood that known and unknown subject attributes (e.g., demographics, baseline characteristics) are evenly balanced across treatment groups, and to enhance the validity of statistical comparisons across treatment groups.

During the Open-Label Titration Phase, subjects will be dosed with CAM2038 q1w until a stabilized dose and adequate analgesic effect has been achieved for at least 2 consecutive weeks prior to randomization to the Double-Blind Treatment Phase, in accordance with pre-defined randomization criteria. Subjects whose pain is controlled on 4 mg, 8 mg or 12 mg CAM2038 q1w during the Open-Label Titration Phase will be maintained on 4 mg, 8 mg or 12 mg CAM2038 q1w, or corresponding placebo, during the Double-Blind Treatment Phase. Subjects whose pain is controlled on 16 mg, 24 mg or 32 mg CAM2038 q1w during the Open-Label Titration Phase will be transitioned to CAM2038 64 mg, 96 mg or 128 mg q4w, or corresponding placebo, during the Double-Blind Treatment Phase. Subjects will be randomized to either active CAM2038 or placebo control in a 1:1 ratio within each of the q1w or q4w regimens.

Under normal circumstances, the blind will not be broken until all participants have completed treatment. In case of emergency, and only if the information is required by the Investigator to ensure subject's safety in managing a medical condition, the treatment may be unblinded at the site by using a code-break module. The code-break module will be provided by the Sponsor or designee. If possible, the Investigator should contact the Sponsor prior to unblinding and after any actions have been taken. Whenever a treatment sequence is prematurely unblinded, the reason, date and time of the unblinding, and the individual who broke the blind, must be documented. Individual code breaks will result in withdrawal of the participant from the study.

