9.5 SECONDARY EFFICACY ENDPOINTS

The secondary efficacy endpoints are as follows:

- Change from baseline in the weekly average of daily WPI scores at Week 12 of the Double-Blind Treatment Phase, based on an NRS-11;
- Percentage of subjects with a 30% and 50% or greater decrease in API from the Open-Label Titration Phase baseline to Week 12 of the Double-Blind Treatment Phase;
- Time to loss of efficacy, defined as discontinuations from the study or study drug for lack of efficacy;
- Change from baseline to Week 12 of the Double-Blind Treatment Phase in the PGI-I scale (as assessed by each subject)
- Change from baseline to Week 12 of the Double-Blind Treatment Phase in WPAI scores;
- Change from baseline to Week 12 of the Double-Blind Treatment Phase in EuroQoL Group EQ-5D-5L scores; and
- Rescue medication days during the Double-Blind Treatment Phase.

9.5.1 CHANGE FROM BASELINE IN THE WEEKLY AVERAGE OF DAILY WPI SCORES AT WEEK 12 OF THE DOUBLE-BLIND TREATMENT PHASE

This variable, based on an NRS-11, will be analyzed via similar methods to those for the primary efficacy variable.

9.5.2 PROPORTION OF RESPONDERS WITH A $\geq 30\%$ AND $\geq 50\%$ REDUCTION FROM THE OPEN-LABEL TITRATION PHASE BASELINE IN API SCORE OVER TIME

Percent reduction from the Open-Label Titration Phase baseline in NRS score to a given post-baseline week will be derived as $100 * (\text{Titration Baseline pain score} - \text{Post-Baseline WAAPI}) / (\text{Titration Baseline pain score})$. A subject is a responder if the percent reduction is at least 30% and 50%.

This variable will be analyzed using the chi-square test. The percentages, the difference of the percentages, and the two-sided 95% confidence interval of the treatment difference will be presented. The 95% confidence intervals of the treatment difference will be calculated using normal approximation.

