9.5.3 TIME TO LOSS OF EFFICACY

Lack of efficacy is defined as discontinuation from the study or study drug for lack of efficacy. The time will be defined as the following:

Discontinuation Date – Randomization Date + 1

Time to loss of efficacy will be analyzed via a log-rank model with treatment effects. The time-to-event “survival” curve will be presented using the Kaplan-Meier method. Median time-to-event and the 95% confidence interval of the median times will be presented, if estimable. In these time-to-event analyses, subjects who do not have the event during the entire study will be censored at Day 84 (end of Week 12 day).

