9.9 POWER AND SAMPLE SIZE JUSTIFICATION

A sample size of 170 subjects per treatment group will provide over 90% power to detect a treatment difference at a two-sided 5% significance level. In the sample size calculation, a treatment difference of 0.7 units and an SD of 2 (or a standardized effect of 0.35) for the primary efficacy variable were assumed.

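### Randomisation is stratified by weekly versus monthly regimen, but the primary MMRM, the responder tests and the log-rank test leave the stratum out; adjusting for it is a free but small gain

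*SAP*

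**What the plan says.** Protocol 8.3: "Randomization will be stratified based on double blind dosing regimen". SAP 4.4 repeats this: "Subjects will be randomized to either active CAM2038 or placebo control in a 1:1 ratio within each of the q1w or q4w regimens". Regimen is the only stratification factor that either document names. It is fixed by the titrated dose: 4, 8 or 12 mg stays weekly, and 16, 24 or 32 mg moves to monthly.

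The analyses do not use it:

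- **Primary MMRM (SAP 9.3):** "The model will include treatment, post-baseline weeks, treatment by week interaction as fixed effects, and baseline WAAPI as the covariate". The SAS code matches the text, with no regimen in the class or model statement.
- **Responder endpoints (SAP 9.5.2 for 30% and 50%, SAP 9.6.1 for 70%):** "This variable will be analyzed using the chi-square test". No strata are named.
- **Time to loss of efficacy (SAP 9.5.3):** "Time to loss of efficacy will be analyzed via a log-rank model with treatment effects".
- **Other secondary and exploratory endpoints** that follow the primary method inherit the omission.
- **Sensitivity analyses (SAP 9.4):** none adds regimen.

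Neither document gives a reason for leaving it out.

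**The concern.** Stratified allocation balances the arms within each regimen, so differences between regimens largely drop out of the true variance of the treatment contrast. A model without regimen still counts those differences as residual noise. If regimen is prognostic beyond baseline WAAPI, the reported standard error overstates the real one, the confidence interval is too wide and the test is conservative.

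Regimen could be prognostic. It separates subjects who needed low doses from those who needed high doses. Starting dose and the rescue ceiling both depend on screening MED (Protocol 8.1.3 and 8.1.4), so regimen may track access to rescue. Visit frequency and windows also differ (Protocol Tables 6 and 7).

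At stake is a little precision for the single primary comparison, and for the responder and time-to-event tests in the fixed sequence of SAP 9.8, where one miss blocks every later claim. The MMRM also relies on data being missing at random; if dropout differs by regimen, conditioning on regimen makes that more plausible.

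**Working it through.** **Inputs from the documents.** 170 per arm, 1:1 allocation, difference 0.7, SD 2.0, and a test "to detect a treatment difference at a two-sided 5% significance level" (SAP 9.9; Protocol 11.4).

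**Inputs assumed.** D, the Week 12 difference between regimens that remains after baseline WAAPI: 0.5 to 1.0 NRS points. f, the share of subjects in one regimen: 0.5 or 0.3. Near-exact 1:1 balance within each regimen, and complete data.

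**1. The plan's own power.** SE = 2 × √(2/170) = 0.217, and 0.7/0.217 = 3.227. Power = Φ(3.227 − 1.960) = 89.7%. Protocol 11.4 says "170 subjects per treatment group will provide 90% power with a 2-sided test at a 5% significance level", which this reproduces. The SAP wording, "A sample size of 170 subjects per treatment group will provide over 90% power", is a rounding matter.

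**2. Effect of omitting regimen.** Total SD is held at 2.0.

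- Share of variance due to regimen: R² = f(1−f)D²/SD²
- Reported SE divided by true SE: r = 1/√(1−R²)
- True alpha, unadjusted: 2 × [1 − Φ(1.96r)]
- Power, unadjusted: Φ(3.227r − 1.96r)
- Power, adjusted: Φ(3.227r − 1.96)

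For f = 0.5 and D = 1.0: R² = 0.25 × 1/4 = 0.0625 and r = 1.0328. Alpha = 2 × [1 − Φ(2.024)] = 4.29%. Power is Φ(1.308) = 90.5% unadjusted and Φ(1.373) = 91.5% adjusted.

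| f | D | R² | r | True alpha, unadjusted | Power, unadjusted | Power, adjusted |
|---|---|---|---|---|---|---|
| either | 0 | 0 | 1 | 5.00% | 89.74% | 89.74% |
| 0.5 | 0.5 | 0.0156 | 1.0079 | 4.82% | 89.92% | 90.19% |
| 0.5 | 1.0 | 0.0625 | 1.0328 | 4.29% | 90.46% | 91.51% |
| 0.3 | 0.5 | 0.0131 | 1.0066 | 4.85% | 89.89% | 90.12% |
| 0.3 | 1.0 | 0.0525 | 1.0273 | 4.41% | 90.35% | 91.23% |

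At f = 0.5 the precision gained is worth about 340 × R² = 5 subjects (D = 0.5) to 21 subjects (D = 1.0).

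**3. Simulation check, f = 0.5, 200,000 stratified trials.** Alpha unadjusted and adjusted: 4.9% and 5.1% at D = 0.5; 4.3% and 5.0% at D = 1.0. Power: 89.8% and 90.1%; 90.3% and 91.4%. In a smaller run (20,000 trials) at D = 0, the two analyses gave the same alpha (4.9%) and the same power (89.3%).

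**4. Secondary tests.** 10,000 trials each, N = 340, 50:50 split, blocks of four, no dropout. The rates are assumed: responders 42% versus 58%, or 50% in both arms under the null; 25% of placebo subjects with the event by Day 84; hazard ratio 0.5. Monte Carlo error on alpha is about √(0.05 × 0.95/10,000) = 0.2 points.

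| Test, unadjusted / stratified | Regimen effect | Alpha | Power |
|---|---|---|---|
| Chi-square / CMH | 20-point responder gap | 4.3% / 5.4% | 83.9% / 86.2% |
| Chi-square / CMH | 40-point responder gap | 2.9% / 5.0% | 85.4% / 90.3% |
| Log-rank / stratified | none | 4.7% / 4.7% | 79.3% / 79.1% |
| Log-rank / stratified | hazard ratio 2 | 4.9% / 5.1% | 79.0% / 79.8% |
| Log-rank / stratified | hazard ratio 4 | 4.0% / 5.1% | 81.3% / 83.9% |

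**The case against.** **The size rests on an assumed D.** Everyone must meet the same pain and rescue criteria before randomisation (Protocol 7.4), the two products are expected to be interchangeable (Protocol 6.2), and baseline WAAPI is already in the model. At D = 0.25 with a 50:50 split, alpha is 4.96% and the gain is 0.1 points of power. This stands: the benefit may be close to nil.

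**Blocking is not described.** The alpha figures need near-exact balance within regimen, and neither document gives a block size. In a simulation with simple 1:1 allocation inside strata, unadjusted alpha was 5.0% (D = 0.5) and 4.9% (D = 1.0), so the conservatism nearly disappears. SAP 4.4's 1:1 ratio within each regimen does suggest balance. Without it the case for adjusting still holds: unadjusted power stays at 89.7%, because 0.217 is then the true standard error, while adjusted power at D = 1.0 is still about 91.5%.

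**Maximum likelihood pushes the other way.** SAP 9.3 uses ML, which slightly understates the variance. A complete-data approximation at N = 340 gives alpha of about 5.10% as planned and 5.14% with regimen added. This can offset the conservatism from a weak regimen effect, so adjustment does not give exactly 5%. The shift is about 0.1 point.

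**The analysis set is not 340.** The mITT Population drops two sites, with the number of subjects not stated. Exclusion may also disturb balance within regimen. Both change the figures a little; neither argues against adjusting.

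**The SAP is already final (version 1.00).** A revision is needed, but SAP 6.2 provides for one.

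**Conclusion.** The concern holds as a minor efficiency point. The design stratifies by regimen, and the primary and key secondary analyses ignore it without a stated reason. The planned tests remain valid: with complete data there is no bias and no inflation of type I error from the omission.

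For a remaining regimen difference of 0.5 to 1.0 points, the primary standard error is 0.7% to 3.3% too large across the two splits, and adjusting adds about 0.2 to 1.0 points of power. The responder tests could gain more, but only if response rates differ widely between regimens. All of this depends on an unstated split, an unstated prognostic strength and near balance within regimen. The omission itself is certain; its practical effect may be zero. The change is optional but worth making, because the planned power of 89.7% has no margin and the adjustment costs almost nothing.

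**What to change.** Before unblinding, issue a version 1.0x revision under SAP 6.2:

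- **Primary MMRM (SAP 9.3):** add regimen as randomised and regimen by week, in the text and the code: `class treatment week subject regimen;` and `model change = treatment week treatment*week baseline regimen regimen*week;`. Carry this into every analysis that follows the primary method.
- **30%, 50% and 70% responders (SAP 9.5.2, 9.6.1):** use a Cochran-Mantel-Haenszel test stratified by regimen, with a stratum-weighted difference in percentages and its 95% CI.
- **Time to loss of efficacy (SAP 9.5.3):** use a log-rank test stratified by regimen.
- **Supportive and descriptive only:** report the Week 12 difference with its 95% CI within each regimen. State that these are imprecise: with SD 2, the half-width is about 0.61 at 85 per arm (50:50 split) and 0.79 at 51 per arm (30% of 170). State also that regimen is set by titrated dose, so a difference between regimens cannot be attributed to formulation alone.

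The cost is SAP wording and code. The stratum is already in the randomisation system and no new data are needed. The MMRM uses 12 more degrees of freedom: 1 for regimen and 11 for regimen by week.

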6.1.3. Double-Blind Phase

Subjects who are stabilized and responding to their CAM2038 q1w dose (4, 8, 12, 16, 24, or 32 mg/week) at the end of the Titration Phase and who fulfill the pre-defined randomization criteria will be randomized to one of two treatment groups in the 12-week Double-Blind Phase:

- Group 1: CAM2038 q1w or CAM2038 q4w SC injections
- Group 2: placebo q1w or placebo q4w SC injections

During the Double-Blind Phase, all subjects who are receiving 4, 8 or 12 mg CAM2038 q1w at the end of the Titration Phase will be randomized to continue their respective CAM2038 q1w dosing of 4 mg, 8 mg or 12 mg CAM2038, or to matching placebo q1w for a total treatment duration of 12 weeks. Subjects who are receiving 16 mg, 24 mg or 32 mg CAM2038 q1w at the end of the Titration Phase will be randomized to CAM2038 q4w (64 mg, 96 mg or 128 mg, respectively) or to matching placebo q4w for a total treatment duration of 12 weeks.

Figure 1: Overview of Study Design

¹ One booster is allowed on Day 3-5 after the first CAM2038, 4 or 8 mg injection. If booster is taken, the next dose on week 2 will be 8 or 12 mg, otherwise stay at 8 mg. Then titration is weekly up to 10 weeks. Final Study Visit is 1 week after the last CAM2038 q1w dose for q1w subjects and 4 weeks after the last q4w dose for q4w subjects. Follow-up is within 4 weeks after the Final study visit.

IR = immediate release; MED=morphine equivalent dose; q1w=once weekly; q4w=once monthly; R= randomization. There will be a Final Study Visit or Early Termination and one Follow-up Call.

Rescue medication, hydrocodone/acetaminophen 5 mg/325 mg q4-6h prn, will be allowed during the Double-Blind Phase (up to three tablets or 15 mg/975 mg/day for subjects whose MED at screening was between 40-79 mg/day and up to six tablets or 30 mg/1950 mg/day for subjects whose MED at screening was ≥80 mg/day). Whenever subjects take rescue medication, they must record their pain intensity “at that moment” prior to taking rescue medication in the electronic diary.

6.1.4. Follow-up Phase for Subjects Not Transitioning to the Open Label Safety Extension Phase

A Final Study Visit will take place 1 week after the last CAM2038/placebo q1w dose or 4 weeks after the last CAM2038/placebo q4w dose. At the Final Study Visit (or early termination), subjects will be transitioned back to standard care or to their treatment prior to study entry. Subjects will then be contacted

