7.3. Criteria for Entry into the Open-Label Titration Phase

In order to be entered into the Titration Phase, subjects must meet the following criteria:

1. After at least a 12-hour washout from the last IR morphine dose, subject must have a COWS ≥ 5 and an API pain score over the past 24 hours ≥ 5 in order to receive a test dose of Buprenex.
2. Passed all baseline criteria, including a normal QTcF, had no change in QTcF > 30 ms at 1 hour after the test dose with Buprenex, and had a COWS score > 5 after the test dose with Buprenex.

Note:

- Subjects on BPN at Screening are required to participate in the down titration and will undergo a washout period prior to the test dose and first on-study treatment. Subjects entering the study on BPN will not transition to IR Morphine, but will refrain from taking their BPN for 12 -24 hours prior to the test dose to achieve the desired washout period.
- Subjects on BPN at Screening are still required to follow the same Day 1 procedures (e.g., confirmation of pain scores, COWS assessment and Buprenex test dose) as non-BPN subjects.

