7.4. Criteria for Randomization into the Double-Blind Phase

For randomization into the Double-Blind Phase, subjects must meet the following criteria at the completion of the Open Label Titration Phase:

1. Been on a stable dose of CAM2038 q1w for at least 2 consecutive weeks.
2. CAM2038 titrated to a dose that provides analgesia (i.e., 7-day API score of ≤ 4 and at least 2 points below the value at the start of Titration Phase) and is well tolerated for 7 days before randomization.
3. Requires no more than an average of one hydrocodone/acetaminophen 5 mg/325 mg/day during the last 7 days prior to randomization.

4. Demonstrated study medication (CAM2038) compliance $\geq 80\%$ during the previous 14 days.
5. Demonstrated daily compliance with pain intensity scoring for ≥ 11 of the previous 14 days, including the last 3 days prior to randomization.

7.5. Inclusion and Exclusion Criteria for Open Label Safety Extension (For Subjects Continuing from the Randomized Double-Blind Phase)

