7.2 DEMOGRAPHIC AND BASELINE CHARACTERISTICS

A summary of demographics and baseline characteristics will be presented by treatment arm and overall for the mITT and the primary Safety Population. The demographic characteristics will consist of age, sex, ethnicity, and race, and will use descriptive statistics.

Demographic data including age, sex, ethnicity, and race, as well as baseline clinical characteristics, will be summarized. Age will be calculated based on the following conditional algorithm:

- Has the subject had his/her birthday this year?
 - Yes; then AGE = (year of informed consent) – (year of birth)
 - No; then AGE = (year of informed consent) – (year of birth) – 1

Since the birth dates capture the months and years only, the days will be imputed as the first day of the month before applying the above rules to derive the ages.

Clinical baseline characteristics summarized will include, at minimum, body mass index, current employment status, duration of low back pain, and pain score at the beginning of the open-label titration phase. Clinical baseline characteristics will be summarized by treatment group and overall.

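### The primary MMRM adjusts only for the on-drug Week 0 score and omits three pre-randomisation variables already held, so it may give up some precision at Week 12

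*SAP*

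**What the plan says.** **Model.** SAP 9.3: "The model will include treatment, post-baseline weeks, treatment by week interaction as fixed effects, and baseline WAAPI as the covariate". The PROC MIXED code there matches. SAP 9.2 defines baseline WAAPI as the mean of the available daily scores in the 7 days before the first randomised treatment, when every subject is still on open-label CAM2038.

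**Range of that covariate.** Protocol 7.4 requires a "7-day API score of ≤ 4 and at least 2 points below the value at the start of Titration Phase".

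**Variables left out.**
- *Titration-start API.* Protocol 7.3 says the "subject must have a COWS ≥ 5 and an API pain score over the past 24 hours ≥ 5" before the test dose, so the score runs from 5 to 10 on the NRS-11. SAP 6.1 defines it as the titration baseline. SAP 7.2 tabulates the "pain score at the beginning of the open-label titration phase", and SAP 9.5.2 and 9.6.1 use it as the denominator of the responder endpoints.
- *Screening MED band* (40-79 or at least 80 mg/day). Screening MED is an eligibility item (Protocol 7.1), and its band sets the starting dose (Protocol 8.1.3).
- *Dosing regimen.* Protocol 8.3 stratifies randomisation by q1w or q4w and by nothing else.

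None of the analyses in SAP 9.4 adds any of the three. Protocol 11.3.2 names no model.

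**Design figures.** Protocol 11.4: "170 subjects per treatment group will provide 90% power with a 2-sided test at a 5% significance level". SAP 9.9: "A sample size of 170 subjects per treatment group will provide over 90% power to detect a treatment difference", assuming "a treatment difference of 0.7 units and an SD of 2 (or a standardized effect of 0.35".

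**The concern.** This is a randomised-withdrawal trial. Protocol 8.1.5 expects that pain may rise in subjects moved to placebo. The one covariate is a well-controlled, on-drug score with a truncated range, which limits how much of the Week 12 variation it can explain. The titration-start score was taken before any CAM2038, so it is a natural candidate to predict how far pain returns. MED band and regimen describe opioid requirement. All three are fixed before randomisation.

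Adjusting for pre-specified prognostic baseline variables narrows the confidence interval without affecting type I error. It is also usual to include a stratification factor in the model, because omitting one that is prognostic tends to leave the model-based standard error slightly too large. What is at stake is the width of the Week 12 interval, in a design with no spare power: the stated inputs give just under 90%, the calculation has no dropout allowance, and the mITT population removes two sites without saying how many subjects that takes out.

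**Working it through.** **1. Reproduce the plan's figure.** Inputs from SAP 9.9 and Protocol 11.4: difference 0.7, SD 2, 170 per arm, two-sided 0.05.
- SE = 2 × √(2/170) = 0.217, and 0.7/0.217 = 3.23.
- Power from the noncentral t with 338 df is 89.6% (normal approximation 89.7%). The normal formula needs 172 per arm for 90%.
- The stated 90% therefore reproduces to rounding. The SAP's claim of more than 90% is marginally high if read literally.

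**2. Effect of added covariates.** Let ρ be the pooled partial correlation of the added covariates, taken together, with Week 12 change, given Week 0 WAAPI. The documents give no value, so a range is shown. SD 2 is treated as the residual SD of the current model. Residual SD = 2√(1 − ρ²), and equivalent n per arm = 170/(1 − ρ²).

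| ρ (assumed) | Variance removed | Residual SD | SE | Power | Equivalent n per arm |
|---|---|---|---|---|---|
| 0 | 0% | 2.000 | 0.217 | 89.6% | 170 |
| 0.1 | 1% | 1.990 | 0.216 | 89.9% | 172 |
| 0.2 | 4% | 1.960 | 0.212 | 90.7% | 177 |
| 0.3 | 9% | 1.908 | 0.207 | 92.1% | 187 |

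The gain is worth about 2, 7 and 17 subjects per arm, and the interval narrows by 0.5%, 2.0% and 4.6% (1 − √(1 − ρ²)).

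**3. If pre-treatment pain predicts only on placebo.** The model has one slope for both arms. With correlation r on placebo and 0 on active, and equal variances, the pooled correlation is r/2 and the pooled R² is r²/4.
- r = 0.3: R² = 0.09/4 = 2.25%, power 90.2%.
- r = 0.4: R² = 0.16/4 = 4%, power 90.7%.

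**4. Cost if the covariates are useless.** Variance inflation is about (340 − 3 − 1)/(340 − 6 − 1) = 336/333 = 1.009, or 0.9%, which costs about 0.3 power points. At ρ = 0.1 (1% removed) gain and cost roughly cancel.

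**5. Fewer subjects at Week 12.** If 150 per arm contribute (assumption), power is 85.6% now, 86.9% at ρ = 0.2 and 88.6% at ρ = 0.3.

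**6. Plausibility of ρ.** An illustrative simulation applied the entry rules to assumed normal scores: start mean 6.5, SD 1.7; Week 0 and Week 12 mean 4, SD 2; correlations 0.2 to 0.5. Week 0 WAAPI kept an SD of about 1.1 and explained 7% to 11% of Week 12 variance. The titration-start score alone added a partial R² of 0.002 to 0.10. These figures illustrate the range; they are not estimates for this trial.

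**The case against.** The strongest reply is that nothing here is an error. The model adjusts for the baseline of its own outcome and is valid under randomisation. Protocol 8.3 says that other baseline factors are expected to balance given the trial's size, and chance imbalance is already reflected in the standard error. That stands: this is a possible gain in efficiency, not a correction of bias.

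Several further points stand and limit the size.
- The titration-start score is a single rating, recorded on paper, taken after washout with a COWS of at least 5, and itself confined to 5-10. Week 12 pain on placebo is measured with rescue available, so the early score is an imperfect guide to it.
- Neither document calls the SD of 2 covariate-adjusted. If it is the raw SD and Week 0 explains 7-11%, current power is already 91.6% to 92.7%, and ρ = 0.2 adds about 1 point.
- The single-timepoint arithmetic only approximates a model with one slope per covariate across all weeks.
- SAP 9 bases pain evaluation on electronic diaries only, so a paper covariate needs an explicit exception.

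A reader might also infer that the rescue ceiling makes MED band prognostic. Protocol 6.1.3 allows "up to three tablets or 15 mg/975 mg/day for subjects whose MED at screening was between 40-79 mg/day" and a higher ceiling for the other band, and 8.1.4 agrees; but 8.1.6 and 8.4 give one maximum with no split by MED. Those sections must be reconciled, and the case should not rest on them.

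A reader might further infer that the omission undermines missing-at-random. No section links these variables to dropout, the MMRM already conditions on observed post-baseline pain, and SAP 9.4 includes tipping-point and random-replacement analyses.

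No objection shows that adding the covariates would harm validity.

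**Conclusion.** The point holds as a low-cost improvement. The primary model uses one range-restricted, on-drug covariate and omits the stratification factor and two other variables already held for every randomised subject. It may give up some precision at Week 12.

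The size rests on assumption: a pooled partial correlation of 0.1 to 0.3, SD 2 as the current residual SD, and 170 per arm contributing at Week 12. On that basis power moves from 89.6% to between 89.9% and 92.1%. If the titration-start score matters mainly on placebo, the gain is likely to be in the lower part of that range.

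Two stronger readings are not supported. One is that the analysis is biased or its type I error inflated; nothing in the documents suggests this. The other is that a loss of precision is established; with no correlation reported, it is only plausible.

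**What to change.** Before unblinding, issue a Version 1.0x revision, which SAP 6.2 provides for, with these changes:

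1. In SAP 9.3, text and code, add regimen stratum (q1w or q4w), titration-start API and screening MED band (40-79 or at least 80 mg/day) alongside baseline WAAPI.
2. State that titration-start API is the site paper score recorded before the test dose, as a named exception to the electronic-diary rule in SAP 9. Protocol 9.3.1 puts this score on paper, and the schedule in Protocol Table 5 dispenses the electronic diary only after the test dose. The responder endpoints already depend on the same score.
3. Carry the same covariates into 9.5.1 and 9.5.7, which borrow the primary method.

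The cost is a few lines of text and code, three degrees of freedom and no new data. MED band and regimen may overlap, since MED band sets the starting dose and regimen follows the titrated dose; that reduces the gain from including both but does not bias the treatment comparison. If the data have already been unblinded, the adjusted model should be reported only as a supportive analysis.
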